10.1.3 Subsequent visits

Only IBS patients will attend subsequent visits. They should be fasting for 6h. The 4dFD should be filled in during the week preceding the visit. Clinical parameters of IBS patients will be recorded.

During subsequent visits, participants will fill in 2 questionnaires:

- IBS-SSS
- IPAQ

BIA will be performed.

10.2 Assessment Types

10.2.1 Clinical parameters

Body length (cm) will be recorded during the first visit.

Body weight (kg), waist circumference (cm), systolic and diastolic blood pressure (mmHg), heart rate (bpm) will be recorded during each visit. Body mass index will be calculated.

10.2.2 Physical Examination

A physical examination will be performed during each visit in order to exclude a possible organic cause of the abdominal symptoms.

10.2.3 IBS status

Presence of IBS will be established based on the ROME IV criteria (appendix 6). IBS will be subtyped according to the predominant stool pattern.

10.2.4 Psychological status

Presence of anxiety, depression and somatization will be evaluated by resp. the PHQ-9, the GAD-7 (Spitzer 2006) and PHQ-15 (Kroenke 2002) (appendices 2-4). Gut-directed anxiety will be assessed by the VSI (Labus 2004) (appendix 1). Evaluation of psychological status will be performed during the first visit.

10.2.5 Symptom severity

Symptom severity will be assessed by the IBS-SSS (Francis 1997) during each visit (appendix 7).

10.2.6 Dietary and FODMAP intake

Dietary and FODMAP intake will be evaluated by the 4dFD (appendix 8) at each visit.

10.2.7 Physical activity

Physical activity will be assessed by the International Physical Activity Questionnaire (IPAQ) (Appendix 5).

10.2.8 Bio-electrical Impedance Analysis

Bio-electrical Impedance Analysis will be performed by trained personnel. BIA will be performed after fasting for at least 6 hours. Subjects should refrain from intensive physical activity the day before the measurement. For women, measurements will be performed outside menstruating periods. Subjects will lay down on an examination couch with bare feet. Any jewelry will be removed. Reactance and resistance will be obtained. Phase angle will be calculated according to the formula:

PhA (°) = (reactance/ resistance° x (180°/ π).

Body composition, including muscle mass and percentage body fat will be calculated.

11 Data Collection and Management

11.1 Monitoring

The study may be inspected by regulatory authorities, including internal audits from the study center of UZ Brussels. The investigators agree by written consent with this protocol to fully co-operate and support audits and inspections compliance checks by allowing individuals to have access to all the study documentation.

11.2 Data Collection

The investigator will ensure careful entry in the CRF of the clinical data required by the study protocol, checking for concordance with the source documents. The CRF will be filled out in English. Correction to the CRF must be carried out by the investigator or a designated member of the staff. All questions in the CRF should be answered in full. The investigator must provide a reasonable explanation of all missing data.

The CRF will be completed and signed by the investigator.

11.3 Database Management and Quality Control

The investigator should ensure the accuracy, completeness, legibility, and timeliness of the data reported to the sponsor in the eCRF and in all required reports.

The investigator must keep source documents for each subject in the study. All information on the eCRF must be traceable to these source documents, which are generally stored in the subject's medical file. The source documents should contain all demographic and medical information, including laboratory data, ECGs, etc., and the original signed informed consent forms.

Data reported on the eCRF that derive from source documents should be consistent with the source documents or the discrepancies should be explained.

The investigator and the sponsor should maintain the study documents as specified in the "Essential Documents for the Conduct of a Clinical Trial" chapter 8 of ICH-GCP and as required by the applicable regulatory requirement(s).

These are documents which individually and collectively permit evaluation of a study and the quality of the data produced and include groups of documents, generated before the study commences, during the clinical study, and after termination of the study and include but are not limited to: study protocol, amendments, submission and approval of EC, raw data of subjects including lab tests, insurance contracts, signed informed consent forms, confidential subjects identification code, eCRF, curricula vitae of the investigator and other participants in the study, study staff lists and responsibilities, monitoring reports and final study report.

The investigator and the sponsor should take measures to prevent accidental or premature destruction of these documents.

The investigator and the sponsor must retain study documents as long as needed to comply with ICH-GCP, national and international regulations. By signing the protocol, the investigator and the sponsor agree to adhere to these requirements.

11.4 Statistical Considerations and Data Analysis

In this explorative study assessing the applicability of BIA as a diagnostic modality or tool for objective evaluation of treatment response, 20 IBS subjects and 20 healthy volunteers will be recruited. Based on the results, a larger study will be considered.

Data collection and analysis will be performed by the study team.

12 Ethical Considerations

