6.5 Rationale for Study Design

The role and significance of bio-electrical impedance analysis has not been studied in IBS. Therefore, we designed this exploratory study to assess its potential role in the diagnosis and follow-up of treatment in IBS.

Study Schematic and Schedule of Activities

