7.3 Endpoints

The primary endpoint of this study is to explore whether PhA differs between IBS patients and healthy volunteers at visit 1.

The secondary endpoints are multiple and are divided in two parts.

The first part explores correlations at initial presentation among IBS patients and healthy subjects:

- Correlation of PhA with IPAQ
- Multiple regression of IBS status with multiple independent variables (PhA, IPAQ, dietary and FODMAP intake, psychological variables, gender)

In the second part, we want to explore changes of PhA according to changes in IBS-SSS in IBS patients only.

8 Investigational Plan

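### A diagnostic purpose is stated for BIA, but no planned analysis measures how well phase angle discriminates IBS patients from healthy volunteers

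*Combined protocol and SAP*

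**What the plan says.** Two sections give the study a diagnostic purpose. Section 6.5 (Rationale for Study Design) says "we designed this exploratory study to assess its potential role in the diagnosis and follow-up of treatment in IBS". Section 11.4 (Statistical Considerations and Data Analysis) describes the study as "assessing the applicability of BIA as a diagnostic modality or tool for objective evaluation of treatment response", states that "20 IBS subjects and 20 healthy volunteers will be recruited", and adds that the findings will inform whether a larger study is undertaken. It gives no criterion for that choice, and names no test, alpha or estimate.

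Section 7.3 (Endpoints) lists the analyses:

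- Primary: "The primary endpoint of this study is to explore whether PhA differs between IBS patients and healthy volunteers at visit 1".
- Secondary, at first presentation: "Correlation of PhA with IPAQ", and a model described as "Multiple regression of IBS status with multiple independent variables (PhA, IPAQ, dietary and FODMAP intake, psychological variables, gender" (the list of predictors ends there).
- Secondary, over time: "we want to explore changes of PhA according to changes in IBS-SSS in IBS patients only".

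The protocol summary in section 2 repeats these and adds a between-group comparison of the faecal microbiome. Neither section mentions an ROC curve, AUC, sensitivity, specificity, cut-off or predictive value.

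**The concern.** A diagnostic question is about individuals: given a PhA value, how well can one tell a patient from a volunteer? A difference in group averages is a different quantity. It can be convincingly non-zero while the two distributions still overlap heavily.

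The regression of IBS status does not fill the gap. It estimates the association of PhA with IBS given the other predictors, and no discrimination output is specified for it. If diet, FODMAP intake and the four psychological scales (GAD-7, PHQ-9, PHQ-15, VSI) are entered separately, it has about nine predictors for 20 patients: PhA, IPAQ, diet, FODMAP, four scales and gender. The VSI items (Appendix 1) ask about abdominal symptoms, so even good discrimination by the whole model could not be credited to PhA.

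The study's stated use is to inform a possible larger one. If the diagnostic half of its purpose is never put on a discrimination scale, that choice is made without the figure that bears on it most directly.

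**Working it through.** **Inputs from the documents:** 20 IBS patients and 20 healthy volunteers (section 11.4), with PhA compared at visit 1 (section 7.3).

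**Inputs assumed, because the documents do not give them:** two-sided alpha of 0.05, two-sample t-test, normal PhA with equal SD in both groups, no dropout. The standardised difference d is varied. The plan gives no derivation of its sample size, so there is no figure of its own to reproduce.

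**Step 1. Smallest observed difference that reaches significance.** d = t(0.975, 38) × √(2/20) = 2.024 × 0.3162 = 0.640.

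**Step 2. What that d means for discrimination, if it were the true value.**

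- AUC = Φ(d/√2) = Φ(0.453) = 0.675 to three decimals, 0.67 to two.
- Sensitivity = specificity at the midpoint cut-off = Φ(d/2) = Φ(0.320) = 0.626, so 1 − 0.626 = 37% of each group is misclassified.
- Overlap of the two distributions = 2 × Φ(−0.320) = 0.75.
- Sensitivity at 90% specificity = Φ(0.640 − 1.282) = 0.26.

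**Step 3. Range of d.** Power is by noncentral t. The AUC interval is AUC ± 1.96 × SE, with the Hanley-McNeil SE at 20 + 20.

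| d | Power | AUC | Approx. 95% CI of AUC | Sens. = spec. |
|---|---|---|---|---|
| 0.50 | 0.338 | 0.638 | 0.465–0.811 | 0.599 |
| 0.64 | 0.505 | 0.675 | 0.507–0.842 | 0.626 |
| 0.80 | 0.693 | 0.714 | 0.554–0.875 | 0.655 |
| 0.91 | 0.800 | 0.740 | 0.585–0.895 | 0.675 |
| 1.50 | 0.996 | 0.856 | 0.735–0.976 | 0.773 |

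An AUC of 0.90 would need d of about 1.81.

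The table reads both ways. A significant result is compatible with weak discrimination. A non-significant result does not rule out something useful: with a true d of 0.80 (AUC 0.71) it occurs 1 − 0.693 = 31% of the time, and at the edge of significance the AUC interval still reaches 0.84.

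**Step 4. What an AUC from 20 + 20 would deliver.** SE² = [A(1−A) + 19(A/(2−A) − A²) + 19(2A²/(1+A) − A²)] / 400.

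- A = 0.70: [0.210 + 19 × 0.0485 + 19 × 0.0865] / 400 = 0.00693, SE = 0.083, 95% CI about 0.54 to 0.86.
- A = 0.80: SE = 0.071, 95% CI about 0.66 to 0.94.

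A half-width of 0.10 at an AUC of 0.80 would need about 39 per group. The planned sample supports an exploratory estimate, not a precise one.

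**The case against.** **The study is exploratory and its formal objective is modest.** Section 7.1 only compares BIA parameters between groups, and section 6.5 says BIA has not been studied in IBS. Asking whether the groups differ before running an accuracy study is a reasonable order. This stands, and it limits the weight of the point.

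**The discrimination information is nearly there already.** Under the normal model the AUC is a one-to-one function of d, so a reported difference with SDs would give it. A Mann-Whitney comparison, equally open because no test is named, yields the empirical AUC as U/(n1 × n2). This also stands. The gap is in what the plan commits to report, and the primary comparison itself is not invalid. But the plan does not commit to SDs or to either test, so the figure is not secured.

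**Stronger readings that the documents do not support.**

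- A reader might infer that a group difference is all that is planned. Section 7.3 also has the regression of IBS status, a correlation, and a longitudinal analysis that serves the treatment-response aim.
- A reader might infer that statistical significance would be taken as proof of diagnostic value, or its absence as disproof. The documents state no alpha, test or decision rule, and section 11.4 refers to the results in general.
- A reader might infer that a significant PhA difference could mean almost no separation. With 20 per group, significance needs an observed d of at least 0.64 under the assumed test. That is weak separation, but not negligible.

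**Conclusion.** The point holds as a mismatch between stated purpose and planned output: sections 6.5 and 11.4 set a diagnostic question, and no listed analysis answers it on a discrimination scale. Its size, under the assumed two-sided 5% t-test and equal-variance normal data, is that a just-significant difference corresponds to an AUC of about 0.67, with about 37% of each group misclassified at the best cut-off. These figures treat the observed d as the true one, and would shift with another test, unequal variances or dropout.

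This is an inexpensive improvement to an exploratory plan. The comparison of groups remains valid, and the treatment-response aim, which section 11.4 offers as an alternative, is unaffected.

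**What to change.** In sections 7.3 and 11.4, add the unadjusted AUC of PhA at visit 1 for IBS patients versus healthy volunteers, with its 95% CI, as an exploratory estimate reported next to the primary difference. State that it will be considered together with the treatment-response results when a larger study is discussed. Its lower confidence limit should not be the sole criterion: with 20 per group an AUC of 0.70 has a lower limit of about 0.54, so such a rule could discard a promising marker through imprecision alone.

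Word any diagnostic conclusion as discrimination from healthy volunteers only. Controls are recruited by advertisement (section 9.1), and suspected organic disease must be ruled out before inclusion (section 9.3), so the study has no comparison group with organic disease and cannot speak to differential diagnosis. If the sponsor prefers not to add the estimate, the alternative is to remove the diagnostic wording from sections 6.5 and 11.4.

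The cost is one further analysis on data already collected, with no new visits or subjects. The downside is a wide interval and a more modest conclusion.

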12.1 Ethical conduct of the study

12.1.1 Declaration of Helsinki

This study will be performed in accordance with the Declaration of Helsinki, International Conference on Harmonisation (ICH) Good Clinical Practice (GCP) guidelines and local laws and regulation as recommended by the European Community.

12.1.2 Ethics Committee

Approval will be obtained from the appropriate regulatory authority in Belgium prior to the start of the study, in this case the Ethical Committee of UZ Brussel. Investigators and personnel are responsible for acting in accordance with their local regulatory requirements.

The study will start on-site only after approval by the local ethical committee.

12.2 Informed Consent

All eligible patients should provide a signed and dated informed consent before inclusion into this study.

12.3 Patient and Study Data Protection

The eCRF will serve as the principal source of data. Source documentation serves to substantiate the integrity of the study data, confirms observations that are recorded and confirms the existence of the study participants.

These data will be checked with adequate precautions to ensure to confidentiality and compliance with applicable data privacy protection laws and regulations. Personnel with responsibilities requiring access to these personal data agree to keep the data confidential.

12.4 Subject Identification

The site will affirm and uphold the principle of the patient's right to protection against the invasion of privacy. Throughout this study and any subsequent data analyses, all data will be identified only by protocol number and ID number.

Only the treating physician will keep the ICF and identity of the patient and healthy subject.

The Data Protection Officer (DPO) will be informed about the database required to perform this study. This included information concerning the goal, the expected number of patients, the type of data that are recorded and the person responsible for the database, according to Belgian regulation.

Appendix 2: General Anxiety Disorder 7 (GAD-7) (Spitzer 2006)

Over the last 2 weeks, how often have you been both-	Not at	Several	Over	Nearly
ered by the following problems?	all	days	half the	every
			days	day
1. Feeling nervous, anxious, or on edge	0	1	2	3
2. Not being able to stop or control worrying	0	1	2	3
3. Worrying too much about different things	0	1	2	3
4. Trouble relaxing	0	1	2	3
5. Being so restless that it's hard to sit still	0	1	2	3
6. Becoming easily annoyed or irritable	0	1	2	3
7. Feeling afraid as if something awful might happen	0	1	2	3

If you checked off any problems, how difficult have these made it for you to do your work, take care of things at home, or get along with other people?

Not difficult at all	
Somewhat difficult	
Very difficult	
Extremely difficult	

Appendix 3: Patient Health Questionnaire-9 (PHQ-9) (Kroenke 2001)

	er the last 2 weeks, how often have you been bothed by any of the following problems?	Not at all	Several days	More than half the days	Nearly every day
1.	Little interest or pleasure in doing things	0	1	2	3
2.	Feeling down, depressed, or hopeless	0	1	2	3
3.	Trouble falling or staying asleep, or sleeping too much	0	1	2	3
4.	Feeling tired or having little energy	0	1	2	3
5.	Poor appetite or overeating	0	1	2	3
6.	Feeling bad about yourself - or that you are a failure or have let yourself or your family down	0	1	2	3
7.	Trouble concentrating on things, such as reading the newspaper or watching television	0	1	2	3
8.	Moving or speaking so slowly that other people could have noticed? Or the opposite - being so fidgety or restless that you have been moving around a lot more than usual	0	1	2	3
9.	Thoughts that you would be better off dead or hurting yourself in some way	0	1	2	3

If you checked off any problems, how difficult have these problems made it for you to do your work, take care of things at home, or get along with other people?

Not difficult at all	
Somewhat difficult	
Very difficult	
Extremely difficult	

APPENDIX 4: Patient Health Questionnaire-15 (PHQ-15) (Kroenke 2002)

During the past 4 weeks, how much have you been bothered by any of the following problems?	Not both- ered at all	Bothered a little	Bothered a lot
1. Stomach pain	0	1	2
2. Back pain	0	1	2
3. Pain in your arms, legs, or joints (knees, hips, etc.)	0	1	2
4. Menstrual cramps or other problems with your periods (women only)	0	1	2
5. Headaches	0	1	2
6. Chest pain	0	1	2
7. Dizziness	0	1	2
8. Fainting spells	0	1	2
9. Feeling your heart pound or race	0	1	2
10. Shortness of breath	0	1	2
11. Pain or problems during sexual intercourse	0	1	2
12. Constipation, loose bowels, or diarrhea	0	1	2
13. Nausea, gas, or indigestion	0	1	2
14. Feeling tired or having low energy	0	1	2
15. Trouble sleeping	0	1	2

Appendix 5: International Physical Activity Questionnaires - Long Form

Part 1 Job-related physical activity

The first section is about your work. This includes paid jobs, farming, volunteer work, course work, and any other unpaid work that you did outside your home. Do not include unpaid work you might do around your home, like housework, yard work, general maintenance, and caring for your family. They are asked in Part 3.

1.	Do you currently have a job or do any unpaid work outside your home? \square Yes		
	\square No \rightarrow Skip to part 2: transportation		
2.	During the last 7 days , on how many days did you do vigorous physical activities like heavy lifting, digging, heavy construction, or climbing stairs as part of your work ? Think about only those physical activities that you did for at least 10 minutes at a time. days per week		
	\square No vigorous job-related physical activity \rightarrow skip to question 4		
3.	How much time did you usually spend on one of those days doing vigorous physical activities as part of your work? hours per day minutes per day		
4.	Again, think about only those physical activities that you did for at least 10 minutes at a time. During the last 7 days, on how many days did you do moderate physical activities like carrying loads as part of your work? Please do not include walking. days per week		
	\square No moderate job-related physical activity \rightarrow skip to question 6		
5.	How much time did you usually spend on one of those days doing moderate physical activities as part of your work? hours per day minutes per day		
6.	During the last 7 days, on how many days did you walk for at least 10 minutes at a time as part of your work? Please do not count any walking you did to travel to or from work. days per week		
	\square No moderate job-related physical activity \rightarrow skip to part 2: transportation		
7.	How much time did you usually spend on one of those days walking as part of your work? hours per day minutes per day		

Part 2: transportation physical activity

These questions are about how you traveled from place to place, including to places like work, stores, movies and so on. 8. During the last 7 days, on how manydays did you travel in a motor vehicle like a train, bus, car, or tram? days per week \square No traveling in a motor vehicle \rightarrow skip to question 10 9. How much time did you usually spend on one of those days traveling in a train, bus, car, tram, or other kind of motor vehicle? _____ hours per day _____ minutes per day Now think only about the **bicycling** and **walking** you might have done to travel to and from work, to do errands, or to go from place to place. 10. During the last 7 days, on how many days did you do bicycle for at least 10 minutes at a time to go from place to place? days per week \square No bicycling from place to place \rightarrow skip to question 12 11. How much time do you usually spend on one of those days to bicycle from place to place? _____ hours per day __ minutes per day 12. During the last 7 days, on how many days did you walk for at least 10 minutes at a time to go from place to place? ____ days per week \square No walking from place to place \rightarrow skip to part 3: housework, house maintaining, and caring for family 13. How much time did you usually spend on one of those days walking from place to place? _____ hours per day minutes per day Part 3: Housework, house maintaining, and caring for family This section is about some of the physical activities you might have done in the last 7 days in and around your home, like housework, gardening, yard work, general maintenance work, and caring for your family. 14. Think about only those physical activities that you did for at least 10 minutes at a time. During the last 7 days, on how many days did you do vigorous physical activities like heavy lifting, chopping wood, shoveling snow, or digging in the garden or yard? days per week \square No vigorous activity in garden or yard \rightarrow skip to guestion 16

15. How much time did you usually spend on one of those days doing vigorous process cal activities in the garden or yard? hours per day minutes per day	hysi-
 16. Again, think about only those physical activities that you did for at least 10 minutes at a time. During the last 7 days, on how many days did you do modate activities like carrying light loads, sweeping, washing windows, and raking the garden or yard? days per week □ No moderate activity in garden or yard → skip to question 18 	
17. How much time did you usually spend on one of those days doing moderate physical activities in the garden or yard? hours per day minutes per day	
18. Once again, think about only those physical activities that you did for at least minutes at a time. During the last days, on how many days did you do modera activities like carrying light loads, washing windows, scrubbing floors and swe ing inside your home? days per week □ No moderate activity inside home → skip to part 4: recreation, sport and lei time physical activity	ate ep-
19. How much time did you usually spend on one of those days doing moderate physical activities inside your home? hours per day minutes per day	
Part 4: Recreation, sport, and leisure-time physical activity	
This section is about all the physical activities that you did in the last 7 days solely for recreation, sport, exercise or leisure. Please do not include any activities you have alr mentioned.	
20. Not counting any walking you have already mentioned, during the last 7 days how many days did you walk for at least 10 minutes at a time in your leisure time? days per week	i, on
\square No walking in leisure time \rightarrow skip to question 22	
21. How much time did you usually spend on one of those days walking in your lessure time? hours per day minutes per day	i-
22. Think about only those physical activities that you did for at least 10 minutes time. During the last 7 days , on how many days did you do vigorous physical tivities like aerobics, running, fast bicycling, or fast swimming in your leisure	ac-

time?

	days per week ☐ No vigorous activity in leisure time → skip to question 24
23	B. How much time did you usually spend on one of those days doing vigorous physi cal activities in your leisure time? hours per day minutes per day
24	Again, think about only those physical activities that you did for at least 10 minutes at a time. During the last 7 days , on how many days did you do moderate physical activities like bicycling at a regular pace, swimming at a regular pace, and doubles tennis in your leisure time ? days per week □ No moderate activity in leisure time → skip to part 5: time spent sitting
25	How much time did you usually spend on one of those days doing moderate physical activities in your leisure time? hours per day minutes per day
Part 5	5: Time spent sitting
ing co	ast questions are about the time you spend sitting while at work, at home, while do- burse work and during leisure time. This may include time spent sitting at a desk, ag friends, reading or sitting or lying down watching television. Do not include any spent sitting in a motor vehicle that you have already told me about.
26	5. During the last 7 days , how much time did you usually spend sitting on a week-day ? hours per day minutes per day
27	7. During the last 7 days , how much time did you usually spend sitting on a week-end day ? hours per day

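### Minor form error: in the IPAQ (Appendix 5), the skip box for walking at work carries the label for moderate work activity, so job-related walking can be under-recorded, missing or mis-entered

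*Combined protocol and SAP*

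**What the plan says.** All of the following is in Appendix 5 of the combined protocol and SAP unless another section is named.

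- **Item 4** asks for days with moderate activity at work and instructs "Please do not include walking". Its skip box is "No moderate job-related physical activity \rightarrow skip to question 6".
- **Item 6** asks "on how many days did you walk for at least 10 minutes at a time as part of your work". Its skip box is "No moderate job-related physical activity \rightarrow skip to part 2: transportation". (The arrow code in both boxes is the form's printed arrow.)
- **Item 7**, which that box passes over, asks "How much time did you usually spend on one of those days walking as part of your work".
- **Items 12 and 20**, the other two walking items, have boxes that name walking: "No walking from place to place" and "No walking in leisure time".

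Section 10.2.7 names Appendix 5 as the instrument for physical activity. Section 7.3 uses IPAQ in two secondary endpoints: the PhA-IPAQ correlation, and the multiple regression of IBS status, where IPAQ is one of several independent variables. Section 6.7 schedules IPAQ at visit 1 and again at the patients' subsequent visits. No section says how IPAQ is scored.

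**The concern.** The box on item 6 names an activity that the form, at item 4, defines as excluding what item 6 asks about. A respondent who follows the print exactly can therefore be routed wrongly. Work walking is recorded only at items 6 and 7, so an error there cannot be put right from the rest of the form.

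At stake is the quality of one input to two exploratory secondary analyses, with 20 patients and 20 healthy volunteers planned (section 11.4). The error is also hard to see afterwards. Section 11.2 asks for complete answers and an explanation of missing data, but a ticked box followed by its printed skip looks like a complete answer and need not raise a query.

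**Working it through.** There is no figure in the plan to reproduce; the check is a comparison of texts.

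**1. Is item 6 the only mismatch?** Items asking for days per week that carry a 'none' box: 2, 4, 6, 8, 10, 12, 14, 16, 18, 20, 22, 24, which is 12. The box names the activity asked about in 11 of them; 12 − 11 = 1 mismatch, item 6. The label shared by items 4 and 6 is the only one printed twice.

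**2. Could it come from reading the PDF?** Unlikely. The two boxes share a label but lead to different places (question 6 and part 2), and each destination suits its own item. One line read twice would repeat the destination as well.

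**3. What does the printed form do to each kind of respondent?** Take people who answer yes to having a job or unpaid work at item 1; the others go straight to part 2.

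| Moderate work activity (not walking) | Walks at work | Is the item 6 box true as printed? | Possible result |
|---|---|---|---|
| Yes | Yes | No | Enters days, answers item 7; recorded |
| No | Yes | Yes | May tick and skip item 7 (time lost), or enter days (recorded) |
| Yes | No | No | No truthful box: writes 0, leaves a blank, or goes on to item 7 and may enter moderate time again |
| No | No | Yes | Ticks; no walking recorded, which is correct |

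Rows 2 and 4 can leave the same mark on the form, a tick with no days, so the record alone cannot separate them.

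**4. Is the lost time picked up elsewhere?** Not as the items are worded. Item 12 covers walking to get from place to place. Item 20 opens with "Not counting any walking you have already mentioned", but asks only about leisure time.

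**5. What can be said about size?** Only a floor for a person in row 2 who ticks the box. Weekly loss = walking days × minutes per day. With the form's own threshold of 10 minutes at a time:

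- 1 day: 1 × 10 = at least 10 min/week
- 7 days: 7 × 10 = at least 70 min/week

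The form sets no upper limit. The documents do not give the number of people in rows 2 and 3, or how they would respond. With no scoring rule and no correlation method stated, no effect on either endpoint can be calculated.

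**The case against.** The strongest case on the other side is that this is a proofreading slip with no demonstrated effect. The question itself asks plainly about walking, and the blank for days comes before the box, so many walkers would simply fill it in. The questionnaires are completed during the visit, and section 11.2 requires full answers. Appendix 5 is in English while Appendices 6 to 8 are marked as Dutch versions, so participants may see a different wording. The text of this form was also not read perfectly: item 18 has lost characters.

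Much of this stands. Loss is possible, not certain, and the form in use has to be checked. The imperfect text does not explain the mismatch, because dropped characters are not a whole phrase with its own skip destination. Completion at the visit is only partial protection, since a ticked skip box does not look like missing data.

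A reader might infer that the error can only under-record activity, and only in people who walk at work. The form does not support that: people with moderate work activity and no work walking (row 3 of the table) may leave blanks or enter moderate time a second time, which would over-record. A reader might also take it that a total IPAQ score is distorted. The documents never say whether a total, a category, a domain or sitting time is analysed.

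**Conclusion.** The label on the item 6 box is wrong as printed, and that can be stated with high confidence. Job-related walking can be under-recorded, missing or mis-entered as a result. How often this would happen, how large it would be, and in which direction it would move either analysis cannot be derived from the documents. The 10 to 70 min/week figures are minimum losses for one affected person, not an estimate of impact.

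A consequence for the PhA-IPAQ correlation and the regression of IBS status rests on two assumptions: that work walking counts in the IPAQ score analysed, and that the form given to participants carries the same wording. The primary comparison of PhA at visit 1 does not use IPAQ and is unaffected. This is a minor point, worth raising because the correction is so cheap.

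**What to change.** Reword the item 6 box to *No job-related walking → skip to part 2: transportation*, in line with items 12 and 20. Check that the language version actually handed out has the corrected wording.

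If the faulty form has already been used:

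- review every record in which the item 6 days or item 7 are blank, whether or not the box is ticked;
- keep any days entered at item 6, including 0;
- if job walking enters the analysed score, report as a sensitivity check whether the two IPAQ analyses change when job walking is left out.

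The cost is one reworded box and a check of the form in use, plus the record review and a small sensitivity check only if faulty forms were completed. Visits, sample size and the primary comparison stay as they are.
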